## 3 Target sample size

The target sample size is 3400 patients with neuropathic pain in total, including 3000 patients with peripheral neuropathic pain (1000 patients with post herpetic neuralgia, if possible, and 2000 patients with peripheral neuropathic pain of the types other than post herpetic neuralgia), and 400 patients with central neuropathic pain (300 patients with post-stroke pain, if possible, and other patients with pain following traumatic spinal cord injury and pain due to Parkinson's disease). For peripheral neuropathic pain, approximately 100 each of patients should be accumulated, if possible, for trigeminal neuralgia, peripheral entrapment neuropathy, iatrogenic neuropathy, neuropathy due to tumor-induced nerve compression or infiltration, posttraumatic pain, and chronic cauda equina syndrome.

[Rationale]

The target sample size of 3400 patients with neuropathic pain is expected to have a 97% probability to detect adverse reactions occurring at the incidence of 0.1% or higher in at least 1 patient. Of the adverse reactions included in the major investigation items, vision-related events are anticipated to develop at the lowest incidence during the survey. In clinical studies of the product conducted in Japan and overseas, the lower bound of the 95% confidence interval for the incidence of this adverse reaction was 6.70% (incidence 7.40%, 380/5134 patients). If this adverse reaction develops at the same incidence as in these clinical studies, this reaction is expected to occur in 227 or more of 3400 patients. Since the safety and efficacy of the product should be evaluated in patients with each type of neuropathic pain, enrollment of the following number of patients will be ensured; approximately 100 patients each, if possible, for trigeminal neuralgia, peripheral entrapment neuropathy, iatrogenic neuropathy, neuropathy due to tumor-induced nerve compression or infiltration, posttraumatic pain, and chronic cauda equina syndrome, approximately 300 patients for post-stroke pain, and a certain number of patients for pain following traumatic spinal cord injury and pain due to Parkinson's disease.

This sample size will also allow for adequate evaluation of the characteristics of other adverse reactions included in the major investigation items. The characteristics to be evaluated include time of onset and duration of adverse reactions, and these were also investigated in the clinical studies.

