## 6.9 Major investigation items

The following events should be evaluated as major investigation items in this survey.

- [1] Peripheral edema and edema-related events
 

Information will be collected about the presence/absence of events related to peripheral edema and the course of patients before and after the onset of events. The situations on development of these events will be analyzed by means of factor analysis, including analysis of the site affected, dose of the product, concomitant therapy, background variables, etc. The package insert gives precautions on congestive heart failure in patients presenting symptoms related to edema. In 30 overseas placebo-controlled studies, the incidence of hypertension and dyspnea was higher in the patients developing peripheral edema than in patients free of peripheral edema, although the incidence of the other events did not differ markedly between these two groups. In view of these facts, information on cardiac function and the incidence of adverse events of the respiratory system will be also collected.
- [2] Dizziness, somnolence, loss of consciousness, syncope and potential for accidental injury
 

Information will be collected about the presence/absence of events related to dizziness, somnolence, loss of consciousness, syncope and potential for accidental injury and the course of patient's condition before and after the onset of events. The situations on development of these events will be analyzed by factor analysis, including analysis of the dose of the product, concomitant therapy, background variables and so on.
- [3] Vision-related events
 

Information will be collected about the presence/absence of events related to the eyes and the course of patient's condition before and after the onset of events. The situations on development of the events will be analyzed by factor analysis, including analysis of the dose of the product, concomitant therapy, background variables and so on.

Patients developing adverse events included in the major investigation items will be

separately investigated in detail if the sponsor deems it necessary.

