8.2.3. Safety analysis

8.2.3.1. Adverse reactions

- All adverse reactions**

Number and proportion of patients with adverse reactions will be tabulated by SOC and PT.

- Serious adverse reactions**

Number and proportion of patients with serious adverse reactions will be tabulated by SOC and PT.

- Details of adverse reactions**

Number and proportion of patients with adverse reactions will be tabulated by SOC and PT for each of the following items.

- Seriousness [Serious, non-serious]
- Expected/unexpected [expected, unexpected]
- Number of days to onset [≤ 4 weeks, >4 to ≤ 13 weeks, >13 weeks]
- Action taken [discontinuation, dose interruption or reduction, dose increase]
- Outcome [not recovered, recovered with sequelae, recovering, resolved/recovered, unknown]

If the same adverse reaction (the same PT) occurs more than once in the same patient, tabulation of the number of patients experiencing the adverse reactions will be handled as follows.

- Seriousness: Serious if both serious and non-serious reactions occurred
- Expected/unexpected: Unexpected if both expected and unexpected reactions occurred
- Number of days to onset: Number of days to onset of the first reaction
- Action taken: If more than one action were taken, select one action in the following order of priority: discontinuation, dose interruption or reduction, dose increase, none
- Outcome: Outcome of the reaction lastly occurred in the patient

- Major investigation items**

Number and proportion of patients will be calculated for the following major investigation items.

- Peripheral edema and edema-related events*^a
*: Adverse events of the cardiovascular and respiratory systems will also be checked.
- Dizziness, somnolence, loss of consciousness, syncope, and potential for accidental injury
- Vision-related events

Furthermore, number and proportion of patients with major investigation items will be tabulated for each SOC and PT by seriousness, action taken and outcome.

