For “peripheral edema and edema-related events”, number and proportion of patients with events will be tabulated by presence or absence of weight increase. Two types of definitions of patients with weight increase are used: 1) those with “weight increased (MedDRA PT)” reported as an adverse reaction; 2) those with body weight increased by 7% or more from baseline at least once. Number and proportion of patients with adverse reactions will be tabulated for each SOC and PT by presence or absence of peripheral edema. In addition, number and proportion of patients with the following adverse reactions will be tabulated by presence or absence of peripheral edema to evaluate the relationship between peripheral edema and cardiovascular and respiratory events.

- Events coded to the MedDRA PT “arrhythmia”, “atrial fibrillation”, “cardiovascular disorder”, “cardiac failure congestive”, “hypertension”, “hypotension”, “palpitations”, “tachycardia”, or “dyspnoea”
- Events coded to the MedDRA SOC “Cardiac disorders”, “Vascular disorders”, or “Respiratory, thoracic and mediastinal disorders”

For “dizziness, somnolence, loss of consciousness, syncope, and potential for accidental injury”, number of days to onset will be tabulated using more specific categories (≤ 4 weeks [1 to 28 days], 1 to 7 days, 8 to 14 days, 15 to 21 days, 22 to 28 days; >4 weeks [≥ 29 days], >4 to ≤ 13 weeks, >13 weeks). In addition, number and proportion of patients with adverse reactions will be tabulated by factor specified in Section 5.4. Tests specified in Section 8.1.3 will be performed to evaluate the relationship between patient demographics, etc. and development of adverse reactions.

Moreover, the median number of days to onset will be tabulated for the following adverse reactions.

- Dizziness
- Somnolence

^a: Occurrence of cardiovascular and respiratory events will be examined in patients with peripheral edema and edema-related events.

- Peripheral edema and edema-related events
- **Pancreas-related events, thyroidal function-related events, change in appetite and activity-related events, suicide-related events, withdrawal symptom and rebound phenomenon-related events, and skin disorder-related events**

Number and proportion of patients will be calculated for each event.

- **Patients with special background**

Number and proportion of patients with adverse reactions and serious adverse reactions will be calculated by SOC and PT in the following subgroups and other patients.

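### The by-factor test of the dizziness item is not split by component, so loss of consciousness, syncope and accidental injury get no factor test of their own

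*SAP*

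**What the plan says.** Protocol 6.9 makes a single major investigation item of "events related to dizziness, somnolence, loss of consciousness, syncope and potential for accidental injury", and plans a factor analysis of it by dose, concomitant therapy and background variables. SAP 2.2 lists factors that affect safety among the things the survey is meant to find.

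SAP 8.2.3.1 does three things for this item. First, "number of days to onset will be tabulated using more specific categories". Second, "number and proportion of patients with adverse reactions will be tabulated by factor specified in Section 5.4". Third, "Tests specified in Section 8.1.3 will be performed to evaluate the relationship between patient demographics, etc. and development of adverse reactions"; these are Fisher's exact test or the exact Cochran-Armitage test, with risk ratio and risk difference. None of these sentences separates the components. The section does separate dizziness from somnolence in one place, where "the median number of days to onset will be tabulated for the following adverse reactions", but loss of consciousness, syncope and accidental injury are not on that list.

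The item is broken down by PT elsewhere in the section, but not by factor: "number and proportion of patients with major investigation items will be tabulated for each SOC and PT by seriousness, action taken and outcome".

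Other tables do show adverse reactions by PT within factor levels:
- SAP 8.2.3.1, special backgrounds (elderly, pediatric, renal and hepatic impairment): "Number and proportion of patients with adverse reactions and serious adverse reactions will be calculated by SOC and PT in the following subgroups" and in the other patients.
- SAP 8.2.3.1: two groups defined by creatinine clearance and initial dose, and target disease by drug class of prior or concomitant medication.
- SAP 8.2.3.5: target disease, and initial dose.
- SAP 8.2.3.4: any Section 5.4 factor that is significant in testing, where the outcome tabulated and tested is at least one adverse reaction.

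Accident-related events are a separate endpoint in SAP 6.1, but the only output named for them is a listing in Section 9.

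**The concern.** On the natural reading of SAP 8.2.3.1 the five-part item is one yes/no outcome per patient. A patient with drowsiness and a patient who lost consciousness count the same. If dizziness and somnolence supply most of the patients, the factor result is essentially theirs, and a factor that acts only on loss of consciousness, syncope or injury barely moves the pooled proportion.

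The route to further PT tables in SAP 8.2.3.4 does not fill the gap, because its screen is broader still. A factor that acts only on a few rare events is unlikely to shift the proportion with any adverse reaction. Such a factor could therefore go through the plan without a test or a PT table on the events it affects, although Protocol 6.9 and SAP 2.2 set out to find factors of this kind.

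**Working it through.** **The plan's own figure.** The sample-size text gives 97% probability of at least one case at 0.1% incidence: 1 − (1 − 0.001)^3400 = 0.967, which reproduces. This concerns seeing one case. It says nothing about finding a factor.

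**Inputs from the documents.** N = 3400 (Protocol 3); two-sided 5% level, exploratory (SAP 4.1); Fisher's exact test (SAP 8.1.3).

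**Assumed inputs.** The documents give no rate for any component of this item. Assume:
- dizziness or somnolence in 20% of patients;
- a factor present in 15% of patients (510 exposed, 2890 not);
- a rare component (loss of consciousness, syncope or injury) with base rate b in the unexposed and b × RR in the exposed;
- the two components independent of each other.

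**Formula.** Pooled proportion = 1 − (1 − common)(1 − rare).

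For b = 0.5% and RR = 4:
- unexposed: 1 − 0.80 × 0.995 = 20.4%
- exposed: 1 − 0.80 × 0.980 = 21.6%
- pooled risk ratio: 21.6 / 20.4 = 1.06
- expected rare cases: 510 × 0.020 + 2890 × 0.005 = 10.2 + 14.5, about 25

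A risk ratio of 4 on the rare events appears as 1.06 on the item.

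**Simulated power of Fisher's exact test** (agreement between runs is within two to three percentage points):

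| Base rate | RR | Effect on dizziness/somnolence | Pooled, unexposed v exposed | Expected rare cases | Power, pooled | Power, rare component |
|---|---|---|---|---|---|---|
| 0.5% | 4 | none | 20.4% v 21.6% | 25 | about 8% | about 85% |
| 0.3% | 4 | none | 20.2% v 21.0% | 15 | about 7% | about 70% |
| 0.1% | 4 | none | 20.1% v 20.3% | 5 | about 5% | about 29% |
| 0.5% | 2 | none | 20.4% v 20.8% | 20 | about 6% | about 27% |
| 0.5% | 4 | 20% relative rise (20% to 24%) | 20.4% v 25.5% | 25 | about 72% | about 86% |

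**Wider range.** A second set of simulations took a common component of 7.4% to 25%, a rare component of 0.1% to 1% overall (3.4 to 34 cases), risk ratios of 3 and 5, and a factor in 20% or 50% of patients. The pooled risk ratio was 1.00 to 1.26 and pooled power 4% to 40%. Power on the rare component alone was 2% to 26% at 0.1%, 24% to 65% at 0.3%, 45% to 87% at 0.5% and 81% to 99% at 1%.

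Two things follow. When the effect is confined to the rare events, the pooled test has little power over most of the range. The separate test is clearly better from about 0.3% upward, but near 0.1% it is weak too.

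**The case against.** The strongest reply is that much is already tabulated. A reader might infer that factors for the rare events cannot be seen at all, and the documents do not support that. Syncope and loss of consciousness, if reported, would appear as separate PT rows by elderly and pediatric status, renal and hepatic impairment, the two clearance and initial-dose groups, target disease, drug class and initial dose, with no significance condition. Major investigation items and accident-related events are listed, serious cases can be investigated in detail, and SAP 8.2.3.5 allows additional analyses. This stands, and it narrows the gap to the absence of any factor test for these events and the absence of PT tables for the remaining factors. Even where PT tables exist, they give single terms and no total for the graver component.

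A reader might also infer from the sample-size text, where "vision-related events are anticipated to develop at the lowest incidence during the survey", that vision ranks lowest only because the rare events are grouped with dizziness. Without component rates this cannot be shown. The text ranks the items as defined, and it treats rare reactions separately through the 97% figure.

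Three further replies have weight. The SAP sentence does not state outright that the table is pooled, although that is its natural reading. The grouping comes from the protocol, and SAP 6.1 defines its events through the European risk management plan, which is not among the documents. All testing is exploratory with no decision rule. These limit the consequence of a missed factor. They do not answer the point, because finding factors is a stated aim of the survey.

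**Conclusion.** The point holds in a limited form. As written, the plan tests Section 5.4 factors for this item only as a whole. Loss of consciousness, syncope and accidental injury get no factor test, and for factors such as sex, body weight, maximum daily dose, inpatient status and hemodialysis they get a PT table only if a still broader screen is significant.

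The size depends on rates that the documents do not give. With 20% dizziness or somnolence, 15% exposed and risk ratio 4, pooled against component power is about 8% v 85% at a 0.5% base rate and 5% v 29% at 0.1%. With risk ratio 2 at 0.5% it is about 6% v 27%. If the factor also raises dizziness and somnolence by a fifth, the pooled test loses little (about 72% v 86%). The loss is therefore serious only when the effect is confined to the rare events and these are not too rare to analyze. This is a cheap improvement to an exploratory analysis. It does not invalidate the item's main incidence tables.

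**What to change.** In SAP 8.2.3.1 keep the pooled item as the total. Add the Section 5.4 factor table, with risk ratio, risk difference, 95% confidence intervals and the exact tests of 8.1.3, for two components:
- (a) dizziness or somnolence;
- (b) loss of consciousness, syncope or accidental injury.

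Produce both for every Section 5.4 safety factor, without a significance screen. Allocate the item's PTs to (a) or (b) in advance and record the allocation in the SAP. State that (b) will be read descriptively with its confidence interval when cases are few. Say explicitly that the existing by-factor table is on the pooled item.

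The data are already collected and coded, so the work is SAP wording, the PT allocation and two more runs of an existing table. The downside is sparse counts and wide intervals for (b). If its incidence is near 0.1%, the separate test will add little and the table's value is mainly descriptive.

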- Age category at the start of treatment [<65 years, ≥ 65 to <70 years, ≥ 70 to <75 years, ≥ 75 to <80 years, ≥ 80 to <85 years, ≥ 85 years]
- Body weight at the start of treatment (by sex) (continuous data)
- Body weight category at the start of treatment (by sex) [<40 kg, ≥ 40 to <50 kg, ≥ 50 to <60 kg, ≥ 60 to <70 kg, ≥ 70 to <80 kg, ≥ 80 to <90 kg, ≥ 90 to <100 kg, ≥ 100 kg]
- Duration of target disease (i.e., diagnosis of neuropathic pain) (continuous data)
- Severity of target disease (i.e., diagnosis of neuropathic pain) [mild, moderate, severe]
- Name of underlying disease (i.e., primary disease of nerve damage that cause neuropathic pain) [by disease name]
- Hepatic impairment [no, yes (mild, moderate, severe)]
- Renal impairment [no, yes (mild, moderate, severe)]
- Hemodialysis [no, yes]
- Creatinine clearance (continuous data)
- Creatinine clearance category [<15 mL/min, ≥ 15 to <30 mL/min, ≥ 30 to <60 mL/min, ≥ 60 mL/min]
- Past medical history [no, yes]
- Complications [no, yes]
- Past medical history or complications of cardiovascular disorder^a [no, yes]
- Past medical history of angioedema^b [no, yes]
- Past medical history or complications (at the start of treatment): Peripheral edema and edema-related events^c [no, yes]
- Past medical history or complications (at the start of treatment): Dizziness, somnolence, loss of consciousness, syncope, and potential for accidental injury^c [no, yes]
- Past medical history or complications (at the start of treatment): Vision-related events^c [no, yes]
- Concomitant medications (at the start of treatment) [no, yes]
- Concomitant use of analgesics^d (at the start of treatment) [no, yes]

^a: Past medical history or complications coded to the MedDRA SOC “Cardiac disorders” or “Vascular disorders”

^b: Past medical history coded to the MedDRA HLT “angioedemas”

^c: The same definition as the major investigation items

^d: The following analgesics will be considered as candidates and identified: drugs classified as “3 digits, 114 antipyretics, analgesics, and anti-inflammatory agents; 3 digits, 113 antiepileptics” in the drug name data file or drugs classified as “Standardised Drug Groupings (SDG), analgesia producing opioids; ATC 3rd level, N06A (ANTIDEPRESSANTS)” in the WHO-drug dictionary.

- Concomitant use of opioid analgesics^a (at the start of treatment) [no, yes]
- Concomitant use of oxycodone or lorazepam^b (at the start of treatment) [no, yes]

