- Elderly patients
- Pediatric patients
- Patients with renal impairment
- Patients with hepatic impairment

Patients with renal impairment are defined as those with “Renal impairment: yes” or creatinine clearance of less than 60 mL/min.

- **Relationship between dosage and administration and development of adverse reactions**

In order to evaluate the relationship between dosage and administration and development of adverse reactions, number and proportion of patients with adverse reactions will be tabulated by SOC and PT for patients whose creatinine clearance and the initial daily dosage are ≥ 60 mL/min and 150 mg, respectively, and patients whose creatinine clearance and the initial daily dosage are ≥ 30 to < 60 mL/min and 75 mg, respectively.

- **Relationship between prior and concomitant medications and development of adverse reactions**

In order to evaluate the relationship between the drug class of prior or concomitant medications and adverse reactions, number of patients with adverse reactions will be tabulated for each PT by target disease (i.e., diagnosis of neuropathic pain) and drug class of prior or concomitant medications. However, concomitant medications used after the initial onset of the event will be excluded from tabulation. For target disease, diseases with number of patients analyzed of approx. 100 or more will be examined.

- **Occurrence of adverse reactions by inclusion in/exclusion from the safety analysis set**

A listing of adverse reactions in patients excluded from the safety analysis set will be prepared. Moreover, number of patients with adverse reactions will be tabulated by SOC and PT.

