8.2.4.7. Exploratory analysis

Response rate of clinical efficacy will be calculated by target disease (i.e., diagnosis of neuropathic pain) and drug class of concomitant medications for factors affecting efficacy. Analyses specified in Sections 8.2.4.2 to 8.2.4.5 will be performed by target disease for each evaluation of efficacy other than clinical efficacy. For target disease, diseases with number of patients analyzed of approx.100 or more will be examined.

Response rate of clinical efficacy will be calculated by subgroup based on the initial dose specified in Section 5.4, and patients demographics specified in Section 8.2.2 will be tabulated for ineffective patients.

Furthermore, additional analyses may be performed as necessary. Results from exploratory analyses will be reported only if they provide important interpretation.

9. Listings

The following listings will be prepared.

- Listing of patients
- Listing of patients with adverse events
- Listing of adverse reactions
- Listing of patients excluded from the safety analysis who experienced adverse reactions
- Listing of serious adverse reactions
- Listing of serious adverse events
- Listing of adverse reactions in patients with hepatic impairment
- Listing of adverse reactions in patients with renal impairment

- Listing of adverse reactions in the elderly
- Listing of adverse reactions (major investigation items)
- Listing of adverse reactions (accident-related events)
- Listing of body weight and laboratory parameters
- Listing of patient-assessed pain score
- Listing of patient-assessed sleep interference score
- Listing of patients' global impression of change (PGIC) and clinical global impression of change (CGIC)
- Listing of administration records
- Listing of initial dose and patient demographics, etc.

The following tables corresponding to appendix forms of periodical safety report will be prepared.

- Appendix Form 3 (Listing of patient summary)
- Appendix Form 2 (Summary of occurrence of adverse reactions and infections)
- Appendix Form 10 (Appendix Form 2-2) (Summary of occurrence of serious adverse events)

10. Appendices

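### The SAP 8.2.3.1 table relating drug class to adverse reactions counts only patients with reactions, without class users or non-users, so by itself it cannot show even the direction of a relationship

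*SAP*

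**What the plan says.** Under the heading on prior and concomitant medications, SAP 8.2.3.1 gives the purpose: "In order to evaluate the relationship between the drug class of prior or concomitant medications and adverse reactions". The output is that "number of patients with adverse reactions will be tabulated for each PT by target disease (i.e., diagnosis of neuropathic pain) and drug class", where the class is that of the prior or concomitant drug. Two conditions follow. On timing: "However, concomitant medications used after the initial onset of the event will be excluded from tabulation". On scope: "For target disease, diseases with number of patients analyzed of approx. 100 or more will be examined". No proportion, number of users, non-user column, test, risk ratio or risk difference is named.

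Elsewhere the plan treats similar questions differently:

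- The dose-relationship table immediately before it in 8.2.3.1 gives number and proportion.
- For efficacy, SAP 8.2.4.7 says: "Response rate of clinical efficacy will be calculated by target disease (i.e., diagnosis of neuropathic pain) and drug class of concomitant medications". By 8.2.4.1 that rate has effective plus ineffective patients as its denominator.
- SAP 5.4 and 8.2.3.4 compare reactions by prior and by concomitant medication, each as any use, yes or no, with tests, risk ratio and risk difference. For the dizziness/somnolence item, 8.2.3.1 also tests the 5.4 factors.
- SAP 8.2.2 defines flags at the start of treatment for particular drugs, such as "Concomitant use of oxycodone or lorazepam", but only to describe the initial-dose groups.
- Protocol 6.9 says that edema events will be examined by factors including "analysis of the site affected, dose of the product, concomitant therapy, background variables, etc", and it names concomitant therapy for the other two major items as well.

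**The concern.** A relationship between a drug class and a reaction is a comparison of risk in users with risk in non-users. A count of reactors who used the class mixes that risk with how often the class is prescribed. Common classes will therefore tend to show the largest counts, and a rarer class with a higher incidence can go unnoticed. SAP 2.2 lists factors affecting safety among the survey's objectives, and this is the only planned safety output that crosses drug class with reactions.

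**Working it through.** **Plan's own figures.** The plan attaches no figure to this table. The illustration borrows one from the sample-size rationale, the vision-related incidence: 380/5134 = 7.40%, as stated. The dependent figure also reproduces: 3400 × 0.0670 = 227.8, against 227 stated.

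**What is known and what is missing.** For one reaction in one target disease, let N be the patients, R the patients with the reaction, a the reactors who used the class, and u all users of the class. SAP 8.2.3.5 supplies N and R by disease, and the table at issue supplies a. Then:

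- risk in users = a/u
- risk in non-users = (R − a)/(N − u)
- RR = the first divided by the second
- 95% CI = RR × exp(±1.96 × √(1/a − 1/u + 1/(R − a) − 1/(N − u)))

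Everything turns on u, which the table does not give. RR equals 1 when u/N = a/R.

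**One count, several answers.** N = 1000 is the postherpetic neuralgia target. R = 74 is 7.4% of 1000. The values a = 20 and u are assumptions.

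| Users u | Risk, users | Risk, non-users | RR (95% CI) | Risk difference, points |
|---|---|---|---|---|
| 100 | 20/100 = 20.0% | 54/900 = 6.0% | 3.33 (2.08 to 5.33) | 14.0 |
| 200 | 20/200 = 10.0% | 54/800 = 6.8% | 1.48 (0.91 to 2.42) | 3.2 |
| 270 | 20/270 = 7.4% | 54/730 = 7.4% | 1.00 (0.61 to 1.64) | 0.0 |
| 400 | 20/400 = 5.0% | 54/600 = 9.0% | 0.56 (0.34 to 0.91) | −4.0 |
| 600 | 20/600 = 3.3% | 54/400 = 13.5% | 0.25 (0.15 to 0.41) | −10.2 |

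The planned cell reads 20 in every row. In a stratum of 100 with R = 7 and a = 3, RR is (3/10)/(4/90) = 6.75 with 10 users and (3/60)/(4/40) = 0.50 with 60 users.

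**Two classes side by side** (all figures assumed). Among 1000 patients, class A is used by 60% with 6% risk: 1000 × 0.60 × 0.06 = 36 reactors. Class B is used by 5% with 12% risk: 1000 × 0.05 × 0.12 = 6 reactors. The counts favour A by 36/6 = 6.0, while the incidence ratio A/B is 0.06/0.12 = 0.5.

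**Can u be taken from elsewhere?** SAP 8.2.2 tabulates a breakdown of prior and concomitant medications, and 8.2.3.5 tabulates the 8.2.2 demographics by target disease. If the second includes the first, and if the breakdown is by class, u is available. The SAP states neither.

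For concomitant drugs a further problem remains. Suppose c reactors started the class only after onset. The timing rule removes them from a, but a breakdown of all use keeps them in u. The user risk becomes a/u instead of (a + c)/u. The non-user risk becomes (R − a)/(N − u) instead of (R − a − c)/(N − u). Both shifts lower the apparent risk ratio. Patients without the event have no onset date, so the rule as written cannot be applied to them.

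Prior medications are not affected. Protocol 6.1 fixes their window at 14 days to 1 day before treatment for everyone.

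**The case against.** The strongest reply is that the information is largely there. Section 8.2.3.5 gives reactions per PT by disease and refers to the 8.2.2 demographics, under which the medication breakdown sits. Section 8.2.3.4 also allows that breakdown within subgroups of factors that test significant, and target disease is a 5.4 factor. Non-user figures would follow by subtraction. Section 8.1.3 says generally that binary data get a proportion, so the word number may be shorthand. All testing is exploratory (4.1), there is no decision rule (4.2), and 8.2.3.5 permits further analyses.

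Much of this stands, and it rules out several stronger readings that a reader might infer:

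- That the relationship cannot be recovered from any planned output. For prior medications it may be recoverable if the by-disease breakdown is by class. The SAP leaves that unclear.
- That concomitant use is not compared at all. Any-use comparisons are planned for all reactions together and for the dizziness/somnolence item.
- That Protocol 6.9 is breached at class level. It promises analysis by concomitant therapy and does not mention drug class.
- That particular drug interactions will be missed. The SAP flags certain drugs but gives no interaction rationale, so the point should not rest on one.

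What does not stand is that these sources repair the table. None crosses drug class with reaction incidence. If number is read as number and proportion, the SAP must still say what the proportion is of and how users are defined among patients without the event.

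**Conclusion.** The point holds for drug class. As written, the table cannot serve its stated purpose: the same count fits risk ratios from 3.33 down to 0.25 in the illustration. That range depends on assumed user numbers and an assumed split of reactors. The conclusion does not, because u is absent whatever its value. The effect is limited to an exploratory safety output, and no primary result changes. It merits correction because the plan gives a denominator in the two closest tables and because the data are already collected (Protocol 6.1 for prior drugs, 6.3 for concomitant drugs).

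**What to change.** In SAP 8.2.3.1, replace the count with the number and proportion of patients with the reaction among users and among non-users of each drug class, within each target disease of about 100 or more patients. Where classes are compared, add risk ratio and risk difference with 95% confidence intervals as in 8.1.3.

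For concomitant drugs, state one exposure rule that applies equally to patients with and without the event. One option is use at the start of treatment, as the 8.2.2 flags already do, with drugs added later but before onset shown in a listing. Prior drugs need no new timing rule.

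The cost is SAP wording and some programming on existing data. Under the start-of-treatment option, drugs added after Day 1 leave the main comparison, which is a real loss and the reason to treat that rule as a choice. Intervals will be wide in small strata: 3 of 10 users against 4 of 90 non-users gives RR 6.75 (1.76 to 25.96). The results should be read as descriptive.
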